Data will be collected prospectively at scheduled time points according to a pre-established case report form (CRF) and stored in REDCap. Baseline evaluation contains characteristic information such as demographics, comorbidities, chronic medications, preoperative lab tests and clinical evaluations, planned surgical procedures, blood pressure, oxygenation saturation before fluid bolus administration. Intraoperative anaesthesia information to be collected include monitored vital signs, anesthetic choice and dose, parameters for mechanical ventilation (tidal volume, positive expiratory pressure delivered, FiO_2), use of open labeled fluids and the use of inotropic drugs and vasopressors, intraoperative complications, procedure characteristics, etc. Postoperative management including the analgesia regimen, transition from the operating room to postoperative anaesthesia care unit (PACU), intensive care unit (ICU), or ward, and any complications of research interest will be documented.

The observation periods start from randomization to 30 days after surgery. Participants are closely monitored until hospital discharge. After discharge, follow-ups are conducted through either in-person hospital visit or telephone calls. Any postoperative complications will be recorded. The observation periods start from randomization to 30 days after surgery. Patients who experience adverse events (AEs) will be monitored until recovery or at least until having any indication of improvement in AE symptoms. All unresolved AEs must be followed up until the outcome is determined, or at least until the final follow-up visit.

All data will be meticulously recorded in CRFs. The principal investigator at each site is responsible for data accuracy. Original documents and test results will be verified before producing electronic versions. Data quality will also be monitored through random checks against original CRFs. An independent Data and Safety Monitoring Board (DSMB), composed of a statistician, CRC, and anesthesiology expert, will oversee the safety and scientific validity of the study.

STUDY OUTCOMES

Primary Endpoint

The primary endpoint is the composite of postoperative complications that occur within 30 days following surgery. Specifically, these complications are

evaluated based on the modified Clavien-Dindo Classification, with those classified as \geq I (as detailed in Table 1) being considered.

Secondary Endpoint

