1. Incidence of hemodynamic instability, which is defined as a mean arterial pressure (MAP) dropping below 65 mmHg or decreasing by more than 20% from the baseline within 20 minutes after the induction of anesthesia.
2. Intraoperative consumption of vasopressors.
3. Length of postoperative hospital stay, calculated as the time interval between the index surgery and the patient's discharge from the hospital.
4. Rate of ideal postoperative recovery, determined as uneventful discharge within 5 days after surgery (without major complications, classified as \geq III according to the Clavien-Dindo classification, incision infection, and readmission);
5. Proportion of patients with Clavien-Dindo classification Grade IV complications, which is defined as life-threatening complications requiring ICU management, such as single organ dysfunction (including dialysis) or multiorgan dysfunction.

Exploratory outcomes

1. Each individual component of the composite primary endpoint (by organ system and by different Clavien-Dindo classification Grades)

2. 30-day all-cause mortality;
3. Incidence of unplanned ICU admission;
4. Incidence of unplanned reoperation;
5. Incidence of in-hospital complications;
6. Barthel index for activities of daily living (ADL) at 30 days after surgery.

Safety Outcomes

1. Incidence of acute kidney injury diagnosed by KDIGO criteria;³¹
2. Massive intraoperative bleeding (hemorrhage exceeds 1000 ml);
3. Episodes of intraoperative hypotension defined as SBP < 90 mm Hg or drop \geq 30% of baseline lasted for 5 min;
4. Episodes of hypertension defined as SBP > 180 mm Hg or rise \geq 30% of baseline lasted for 5 min;
5. Arrhythmia that consisted of bradycardia (heart rate < 40 beats per minutes), tachycardia (HR > 100bpm) or new onset of arrhythmia that require anti-arrhythmic drugs;
6. Airway hyper-responsiveness defined as a airway peak pressure > 40cm H₂O).

All outcomes will be discussed and evaluated by the endpoint assessment committee and documented as appropriate. All adverse events must be recorded in CRFs and documented. The reporting of SAE follows the

institutional requirement and local regulations.

STATISTICAL ANALYSIS PLAN

Scope of the Analysis plan

This Statistical Analysis Plan (SAP) presents the statistical consideration in design and analyses for COIN trial. The final manuscript will strictly follow this SAP.

Sample Sizes

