To better interpret the composite endpoints with different levels of clinical importance. We will repeat analysis of primary outcome using a hierarchical global rank scale by using win ratio method. This method put the greater weight on the more patient centered outcomes with more clinical relevant outcomes (death, life threatening complications) than transient, self-limiting complications. In the present study, the complications with higher grade of Clavien-Dindo classification will be put on higher hierarchy. The global rank endpoint will be constructed by comparing each patient in the intervention group to each patient in the control group (a total of $m \times n$ comparisons where m is the total number of patients in the intervention group and n the number of patients in the standard care group) for the prespecified order of the endpoints. Based on which patient performs better in each pair, the group they belong to would be declared the 'winner'. This would give us the total number of winners in each group and our test statistic would be based on this. In the case of the win-ratio method, for instance, the statistic would be the number of winners in the intervention group divided by the number of winners in the control group. A 95% confidence interval for the win ratio will be calculated with the bootstrap

method. To make the pairwise comparison, the priority order of endpoints are:

1. Clavien-Dindo grade V
2. Clavien-Dindo grade IVb
3. Clavien-Dindo grade IVa
4. Clavien-Dindo grade IIIb
5. Clavien-Dindo grade IIIa
6. Clavien-Dindo grade II
7. Clavien-Dindo grade I
8. No complications happened

Finally, We will repeat primary analysis on primary endpoints by using mITT, as-treated and PP data-sets.

For scenarios where events are rare in the defined order above, the following orders and composites shall be considered:

1. Clavien-Dindo grade V
2. Clavien-Dindo grade IV
3. Clavien-Dindo grade III
4. Clavien-Dindo grade II
5. Clavien-Dindo grade I
6. No complications happened

OR

1. Clavien-Dindo grade V
2. Clavien-Dindo grade III - IV

3. Clavein-Dindo grade I - II
4. No complications happened

Estimating the effect of the intervention for participants who undergo surgery under general anesthesia

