Rate of ideal postoperative recovery within 5 days of surgery will be analysed using a logistic regression model, adjusting for planned surgical procedure complexity grade, ASA grade, gender, age, baseline hemoglobin, and baseline creatinine. Similar will be conducted for as above for cases of computing complexities.

Analyses of exploratory outcomes

Each individual component of the composite primary endpoint (by organ system and by different Clavien-Dindo classification Grades)

This will be analyzed using the same approach as for the analysis of the primary outcome above. Unadjusted Chi - squared test will be used.

Thirty day all-cause mortality

The expected event rate for this endpoint is extremely low. Thus, descriptive statistics will be used. Fisher exact test will be used to compare between group difference.

Incidence of unplanned ICU admission;

This outcome will be compared either using Chi-square test or Fisher exact test as appropriate depending on rate.

Incidence of unplanned reoperation

This outcome will be compared either using Chi-square test or Fisher exact test as appropriate depending on rate.

Incidence of in-hospital complications

This outcome will be compared either using Chi-square test or Fisher exact test as appropriate depending on rate.

Barthel index for activities of daily living (ADL) at 30 days after surgery.

The ADL score will be analyzed using a linear mixed model, with a random intercept for participant centers and adjusting for planned surgical procedure complexity grade, ASA grade, age, gender, baseline hemoglobin, and baseline creatinine. For any computation complexities, variable transformations or dimension reduction methods will be used.

Clavien-Dindo Grade IV - V complications within 30 days of surgery

Clavien-Dindo Grade IV - V complications within 30 days of surgery will be analyzed using a logistic regression model, adjusting for planned surgical procedure complexity grade, ASA grade, baseline hemoglobin, and baseline creatinine.

The expected event rate for this endpoint is lower than for other outcomes, thus we reduce the number of covariates that included in the model.

Analysis of Safety outcomes

Safety outcomes will be analyzed using the same method as the analysis of primary endpoints.

Interim analyses and stopping rules

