Grade III	Requiring surgical, endoscopic, or radiological intervention
Grade IIIa	Intervention not under general anesthesia
Grade IIIb	Intervention under general anesthesia
Grade IV	Life-threatening complication (including central nervous system complications) requiring IC/ICU management
Grade IVa	Single organ dysfunction (including dialysis)
Grade IVb	Multiorgan dysfunction
Grade V	Death of a patient

Figure 1 Study Flowchart

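### Grade V (death) is tested by chi-squared as a component of the composite, while 30-day mortality, essentially the same event, gets Fisher's exact test; rare components have no exact-test fallback

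*SAP*

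**What the plan says.** The SAP lists as its first exploratory outcome "Each individual component of the composite primary endpoint (by organ system and by different Clavien-Dindo classification Grades"). In Analyses of exploratory outcomes the method is given in two sentences: "This will be analyzed using the same approach as for the analysis of the primary outcome above", then "Unadjusted Chi - squared test will be used". No alternative is offered there for sparse counts.

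The entry directly below, Thirty day all-cause mortality, reasons differently: "The expected event rate for this endpoint is extremely low". It therefore plans descriptive statistics, and adds "Fisher exact test will be used to compare between group difference".

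Table 1 defines Grade V as "Death of a patient", with no requirement that the death be attributed to a complication. The window is the same as for the mortality outcome: "The primary endpoint is the composite of postoperative complications that occur within 30 days following surgery".

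The three entries that follow mortality (unplanned ICU admission, unplanned reoperation, in-hospital complications) each allow either chi-squared or Fisher's exact test, the choice depending on the event rate.

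On the ordering of grades, Secondary Analyses of the primary endpoint plans a win ratio: "In the present study, the complications with higher grade of Clavien-Dindo classification will be put on higher hierarchy". The component entry sets no at-or-above thresholds. It also does not say whether a patient counts once, at the worst grade, or under every grade experienced.

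**The concern.** Two adjacent entries assign different tests to what is essentially one event. The SAP recognises that deaths will be sparse in the mortality entry but makes no allowance for it in the component entry. The same gap covers any other rare row of the component table, such as Grade IV or an uncommon organ system.

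The composite counts Grade I events, so readers will turn to the component table to see what drives the result. If it shows one P value for Grade V and the mortality row shows another, possibly across 0.05, the report contradicts itself on the most serious outcome while following the plan exactly.

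A second, smaller issue is that the grades are ordered but are compared one at a time. If patients are counted at their worst grade, someone moved from Grade II to Grade I leaves one row and enters another. A Grade I row read alone can then point the wrong way.

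**Working it through.** **Inputs.** 1010 per arm comes from the SAP, Sample Sizes; after the stated 10% drop-out this is 1010 × 0.90 = 909. The SAP gives no death rate and no grade-specific rates, so every count and rate below is an assumption. No figure of the plan's own bears on this point.

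**1. Same event, two tests.** Grade V is death, the composite window is 30 days, and the mortality outcome is all-cause at 30 days. The component entry gives chi-squared; the mortality entry gives Fisher's.

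For a v b deaths with n per arm, the uncorrected Pearson statistic is

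χ² = (a − b)² × 2n / [(a + b)(2n − a − b)], on 1 degree of freedom.

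For 4 v 0 and n = 1010: χ² = 16 × 2020 / (4 × 2016) = 4.008, P = 0.045.

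Fisher's two-sided P for 4 v 0 is 2 × (1010 × 1009 × 1008 × 1007) / (2020 × 2019 × 2018 × 2017) = 2 × 0.0623 = 0.125.

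| Deaths (1010 per arm) | Expected per arm | χ² | Chi-squared P | Fisher P | Same side of 0.05? |
|---|---|---|---|---|---|
| 3 v 0 | 1.5 | 3.004 | 0.083 | 0.250 | yes |
| 4 v 0 | 2.0 | 4.008 | 0.045 | 0.125 | no |
| 5 v 0 | 2.5 | 5.012 | 0.025 | 0.062 | no |
| 6 v 0 | 3.0 | 6.018 | 0.014 | 0.031 | yes |
| 6 v 1 | 3.5 | 3.584 | 0.058 | 0.124 | yes |
| 7 v 1 | 4.0 | 4.518 | 0.034 | 0.070 | no |
| 8 v 1 | 4.5 | 5.469 | 0.019 | 0.039 | yes |
| 9 v 2 | 5.5 | 4.479 | 0.034 | 0.065 | no |

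With 909 per arm, each of these P values changes by no more than about 0.0001. The P values differ in every row; they fall on opposite sides of 0.05 only at particular counts. In all but the last row the expected count is below 5, where the chi-squared approximation is usually thought unreliable.

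**2. Exact grades when severity shifts.** Assume worst-grade counting, 1010 per arm, and control rates of I 12%, II 15%, III 4%, IV 1.5%, V 0.5% (sum 33%).

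- *Pure downgrading*: 20% of Grades II, III and IV move down one grade and none is prevented. Grade I becomes 12% + 0.20 × 15% = 15%, that is 121 v 152 patients, risk ratio 1.25, P = 0.044 against the treatment. Grades II, III and IV all fall (risk ratios 0.85, 0.88, 0.80).
- *Same, but 20% of Grade I is also prevented*: Grade I becomes 9.6% + 3% = 12.6%, that is 121 v 127, risk ratio 1.05, P = 0.68.
- *Uniform risk ratio of 0.8*: every grade falls, and Grade I goes from 121 to 97.

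The result depends on the assumed mix. Under pure downgrading, Grade I at 20% with Grade II at 10% gives risk ratio 1.10, P = 0.27; Grade I at 8% with Grade II at 19% gives 1.48, P = 0.005. If 20% of Grade I is also prevented, these become 0.90 and 1.28.

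**The case against.** **A general rule already exists.** General analysis Principles allows chi-squared or Fisher's exact test for categorical variables. This softens the point but does not remove it, because the later entries name one specific test each, and a named test governs.

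**The conflict needs particular counts.** This is right. With no deaths in one arm, only 4 or 5 in the other put the two tests on opposite sides of 0.05. The figures also use the uncorrected chi-squared; with a continuity correction, 4 v 0 gives 0.133 and 5 v 0 gives 0.073, both non-significant like Fisher's. The SAP does not say which version applies, so the conflict is possible rather than assured.

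**Downgrading as harm.** A reader might infer that per-grade testing must make a severity-reducing treatment look harmful in the lower grade. The SAP does not support that. It happens only when more patients enter a grade from above than leave it, and it presumes worst-grade counting, which the SAP does not state. The design expects complications to fall overall, from 33% to 26%; under a uniform reduction the effect is absent. The win ratio already credits a move from II to I, and a separate Grade IV–V model supplies one cumulative threshold. What remains is that neither corrects a Grade I row read by itself.

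**Zero cells.** A reader might also infer that the risk ratio is left undefined when one arm has no deaths. It is not: Analysis of the primary endpoints, whose approach the components inherit, permits other approximations or numerical methods besides the log-normal one.

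**Conclusion.** The point holds in a limited form. The SAP assigns chi-squared to Grade V and to every other component, however rare, and Fisher's exact test to 30-day mortality, so two P values would be reported for essentially the same deaths. At 4 v 0, 5 v 0, 7 v 1 or 9 v 2 deaths they would fall on opposite sides of 0.05, given the uncorrected statistic and 1010 per arm. The counts are assumed, since the SAP gives no mortality rate.

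The ordering of grades is a reporting weakness: exact-grade comparisons can mislead under worst-grade counting and a mainly downward shift in severity, but need not.

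Both parts are minor. The SAP calls everything beyond the single primary analysis exploratory and hypothesis-generating, and the primary conclusion does not depend on either.

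**What to change.** 1. In the component entry, replace the fixed chi-squared test with the rule used for the neighbouring outcomes: chi-squared or Fisher's exact test according to event rate. State that Grade V uses Fisher's exact test, so that it and 30-day mortality give one P value.

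2. Give the grade breakdown at cumulative thresholds (II or higher, III or higher, IV or higher, V) beside the primary endpoint and the win ratio, and show exact grades as counts without tests. A patient with any event at or above a threshold also has a worst grade at or above it, so these rows do not depend on the unstated counting rule. A footnote should give the rule used for the exact-grade counts.

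The cost is a few lines of SAP wording and a revised table shell. No new data are needed, and the sample size and primary analysis are untouched.

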In order to detect a 13% absolute reduction (from 33% to 26%) for the primary outcome of postoperative complications of Clavien-Dindo Grade \geq I up to 30 days after surgery (a risk ratio of 0.8), with 90% power and an overall type I error rate of 5%, a total of 2020 patients (1010 per arm) are required, accounting for 10% drop-out rate.

Randomisation procedure

Randomisation will occur after obtaining informed consent from the eligible patients and shortly before the index surgical procedure is due to start (last-minute randomization). Patients will be centrally allocated to treatment arms in a 1:1 ratio by permuted block randomization stratified with participant centers. To enter a patient into the COIN trial, research staff at each participant site will log on to a secure web-based randomization platform of Redcap data

entry system and obtain a unique patient identification number and allocation assignment. This information will be only revealed to the unblinded investigator who prepare the intervention fluids.

Datasets for Analyses

All statistical analyses within this study will be performed following the intention-to-treat principle. This implies that patients will be analysed in accordance with the treatment groups to which they were initially assigned, as depicted in Figure 1. It is expected that there will be either no or very minimal losses to follow-up for primary and secondary outcomes considering the prospective feature. Patients with missing primary outcome data will be excluded from the analysis (complete-case analysis approach). Missing data for baseline covariates to be included in the analysis model will be accounted for using multiple imputation.

Participation of individual patient in the study will be terminated if they (or their trusted person) withdraw consent. However, if the investigator discontinues the patient's participation, either temporarily or permanently, for reasons in the patient's best interest, especially when serious adverse events are suspected to be related to the intervention, the patient will remain in the analysis to uphold the intention-to-treat principle. Their data will continue to be collected until 30 days after surgery, which marks the final follow-up.

Modified Intent-to-Treat (m-ITT) population excludes individuals who had their

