surgical procedures canceled after randomization, patients who withdrew their consent. The as-treated population is defined by the treatment that was actually received during the trial. This takes into account any deviations from the initially assigned treatment regimen, such as crossovers to the other treatments. The Per-Protocol (PP) population consists of all patients who received the assigned treatment without significant deviations from the protocol. Specifically, the analysis will be restricted to those who completed the full-term intervention as it was initially assigned. Participants with treatment interruptions will be excluded from the PP analysis. The exclusion list will be verified by the steering committee prior to lock of the database. Analyses conducted on these dataset will be treated as supplementary analyses.

General analysis Principles

The COIN trial is designed to assess the impact of preoperative colloid infusion on the occurrence of postoperative complications in surgical patients undergoing non-cardiac surgery with general anesthesia. The estimand is the difference in the incidence of postoperative complications as defined by higher than grade I Clavien-Dindo classification at 30 days after surgery between Colloid bolus administration versus crystalloid bolus administration, in patients undergo elective non-cardiac surgery under general anesthesia. The target population is patients experienced surgery procedure. The patients have the planned surgery canceled after randomization will be excluded from the

primary analyses.

In general, categorical variables are to be compared using χ^2 test or Fisher's exact test. Continuous variables will be compared via t-test or Wilcoxon's rank-sum test. Variable normality will be assessed either via the Shapiro-Wilk test or QQ-plots and residual plots. Variable transformation such as natural logarithm or square root will be applied where necessary, or non-parametric methods (such as Wilcoxon rank sum test) shall be applied.

For the analyses of primary, secondary outcomes, and the process measures, the following information will be presented:

- 📅 The number of patients included in each analysis, by treatment arm
- 📅 A summary statistic of the outcome (such as, number (%), mean (sd), media (IQR), etc), by treatment arm
- 📅 The estimated treatment effect
- 📅 A 95% confidence interval for the estimated treatment effect
- 📅 A two-sided P value

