The COIN trial is to evaluate whether colloid bolus infusion before anesthesia induction improves clinical outcomes compared to crystalloid bolus infusion in patients undergoing non-cardiac surgery under general anaesthesia. In clinical practice, in rare circumstance, surgery may be delayed or canceled, and the participant may not undergo surgery before the outcome is collected. Similarly, in rare instances, the surgery may be conducted under local anesthesia. These participants will be excluded and the left participants who undergo surgery will be analyzed as mITT datasets.

Protocol Deviations

The number and percent of patients with at least one protocol deviation will be summarized for each treatment arm. These include received wrong fluid, received wrong dose of fluid, or with infusion duration exceeds 15 min. These participants will be excluded and the left participants will be analysed as PP datasets.

Analysis of the secondary endpoints

Incidence of hemodynamic instability within 20min of anesthesia induction.

Incidence of post-induction hypotension will be analysed using a logistic regression model, adjusting for ASA grade, gender, age, NPO duration, fluid administration within 12 hours prior to surgery (y/n), history of hypertension.

Intraoperative consumption of vasopressors

Intraoperative consumption of vasopressors will be analyzed using a linear regression model, adjusting for ASA grade, gender, age, NPO duration, fluid administration within 12 hours prior to surgery (y/n), history of hypertension.

Length of postoperative hospital stay

Length of postoperative hospital stay will be analysed using a competing-risk time-to-event model, considering mortality as a competing risk for hospital discharge. The model will include adjustment for planned surgical procedure complexity grade, ASA grade, gender, age, baseline hemoglobin, and baseline creatinine. In case of convergence issues, singular matrix, or other numeric complexity, appropriate data transformation, or dimension reduction methods will be used.

For each treatment arm, we will present median and IQR for length of hospital stay for patients survived to hospital discharge. The number and percentage of patients survived to discharge and number and percentage of patients who died will also be reported.

Rate of ideal postoperative recovery within 5 days of surgery

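### Safety outcomes are analysed by assigned arm only, so harm after a wrong study fluid is counted against the fluid not given, and the place of exposed patients whose surgery is cancelled is unclear

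*SAP*

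**What the plan says.** Under Analysis of Safety outcomes, the SAP says only: "Safety outcomes will be analyzed using the same method as the analysis of primary endpoints".

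Datasets for Analyses sets the general rule: "All statistical analyses within this study will be performed following the intention-to-treat principle", meaning that "patients will be analysed in accordance with the treatment groups to which they were initially assigned". The same section keeps in the analysis any patient whose participation the investigator stops, with particular mention of suspected related serious adverse events.

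That section also defines further sets. For one of them, "The as-treated population is defined by the treatment that was actually received during the trial". Analyses on these sets are called supplementary. The only place that schedules them is Secondary Analyses of the primary endpoint: "We will repeat primary analysis on primary endpoints by using mITT, as-treated and PP data-sets".

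General analysis Principles adds that "The target population is patients experienced surgery procedure", and that "The patients have the planned surgery canceled after randomization will be excluded from the" primary analyses.

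Protocol Deviations lists the foreseen departures: "These include received wrong fluid, received wrong dose of fluid, or with infusion duration exceeds 15 min". These patients are removed from the per-protocol set.

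**The concern.** A safety analysis should attribute harm to the agent the patient received. Under an assigned-arm rule, a crystalloid patient given starch in error who then develops acute kidney injury counts as a crystalloid case, and the reverse error does the opposite. Both errors shrink the apparent difference between the fluids. For efficacy that dilution is accepted as the price of keeping the randomised comparison. For safety it works in the unsafe direction, because it makes a real harm harder to see.

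A second matter is the denominator. The bolus is completed before induction, so a patient can be exposed and then not be operated on. If the SAP does not say whether that patient counts for safety, the choice can be made after the data are known.

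**Working it through.** The SAP gives no rate of wrong-fluid errors, of cancellations or of safety events, so there is no figure of its own to reproduce on this point. The check is a reading of the text plus one illustration on assumed rates.

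**Which arm a wrong-fluid patient counts in**

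1. Datasets for Analyses: all analyses go by assigned group.
2. Analysis of Safety outcomes: same method as the primary endpoint, with no separate population.
3. Secondary Analyses of the primary endpoint: the as-treated and per-protocol sets are scheduled for the primary endpoint. No section schedules them for safety.
4. Protocol Deviations: wrong fluid is an expected type of deviation.

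A wrong-fluid patient is therefore counted in the assigned arm for every listed safety outcome, and no scheduled safety table shows otherwise. This holds whether the safety sentence means only the test or the whole primary-endpoint approach.

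**Size of the dilution**

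Let d be the true difference in event rate between the fluids, and let a share c of each arm receive the other study fluid, with the same risk as others given that fluid. The assigned-arm difference is then

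d × (1 − 2c).

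Assumed rates: 4% and 2% by fluid received, so d = 2.0 points. The SAP gives 1010 per arm. Power is for a two-sided 5% comparison of two proportions.

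| Wrong fluid in each arm (assumed) | Rates by assigned arm | Difference (points) | Power |
|---|---|---|---|
| 0 | 4.00% v 2.00% | 2.00 | 75% |
| 0.5% | 3.99% v 2.01% | 1.98 | 74% |
| 1% | 3.98% v 2.02% | 1.96 | 73% |
| 2% | 3.96% v 2.04% | 1.92 | 72% |
| 5% | 3.90% v 2.10% | 1.80 | 66% |

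For the 1% row: 0.99 × 4% + 0.01 × 2% = 3.98%, and 0.99 × 2% + 0.01 × 4% = 2.02%.

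**Whether an exposed patient without surgery counts**

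- Datasets for Analyses: all analyses are intention-to-treat, and patients stopped for suspected related serious events remain.
- General analysis Principles: cancelled surgery is excluded from the primary analyses.
- Secondary Analyses of the primary endpoint: the modified set, which is the one that drops cancellations, is a repeat of the primary analysis, so the primary analysis itself should include them.

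The second statement conflicts with the first and third. Safety is tied to the primary endpoint by a single phrase, so the text does not settle which rule it follows.

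**DSMB**

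Interim analyses and stopping rules has the board compare safety outcomes between groups by a rank-sum test at P of 0.05 or less. It names no analysis set either.

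**The case against.** The best counter-argument concerns cancelled surgery. A reader might infer that safety drops every patient whose operation was cancelled, and so loses the very harms the fluid causes most directly. The SAP does not support that inference:

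- Analysis of the primary endpoints contains a test and effect measures, not a population rule. Same method can fairly be read as the test alone.
- The exclusion of cancellations is limited to the primary analyses, and safety is not one of them.
- Patients stopped for suspected related serious events are expressly kept.
- A reaction to the bolus is not one of the six listed safety outcomes. Several of these, such as massive intraoperative bleeding, presuppose an operation.

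What stands is narrower: the rules conflict and the safety population is not fixed.

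A reader might also infer that the DSMB's safety stopping rule inherits the problem. That too goes beyond the text, since the rule sets its own test and does not refer to the safety analysis section. The board can also stop the trial at any point.

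On wrong fluid, it is fair to say that the effect is slight. The treatment is a single bolus prepared by one unblinded investigator, so errors should be rare and do not accumulate over time. It is also true that the as-treated set is defined in general terms, and nothing forbids using it for safety. But nothing schedules it either, and the point about attribution remains.

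**Conclusion.** The concern holds in two parts of different strength. That safety is analysed by assigned arm alone, with wrong-fluid harms credited to the fluid not received, follows directly from the text. The unclear position of exposed patients without surgery is an ambiguity arising from conflicting rules, not a stated exclusion.

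The direction of the first part is toward no difference, provided that wrong fluid means the other study fluid. Its size is probably small: on the assumed 4% and 2%, errors of up to 2% per arm cost at most 0.08 points of a 2.0-point difference and 3 to 4 percentage points of power. The second part cannot be sized from the SAP, which describes cancellation as rare. Neither part affects the primary efficacy analysis. The point is worth making because the correction is cheap and fixes the safety population in advance.

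**What to change.** In Analysis of Safety outcomes, state that:

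- safety shares only the statistical test and effect measures with the primary endpoint;
- the safety set is all randomised patients in whom any study fluid was started, grouped by the study fluid actually received, whether or not surgery followed;
- outcomes that can occur only during an operation are limited to patients who were operated on;
- patients without surgery have a stated 30-day end date, since the SAP now counts follow-up from surgery;
- the assigned-arm safety table is given as a supplement.

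In Interim analyses and stopping rules, name the same set for the DSMB's safety review.

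The cost is one paragraph, one extra table and a follow-up rule for the few patients without surgery. Observation already starts at randomisation and adverse events are already recorded. There are two drawbacks: the safety and efficacy denominators will differ slightly, and a comparison by fluid received is no longer strictly randomised, which is why the assigned-arm table should stay beside it.
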